**C.7. Enhanced Intervention Versus Usual Care Group:**

*Group 1: Enhanced Intervention Group with Patient Navigation and Social Worker:* Patients randomized to Group 1 will be provided a list of eye care providers to choose from for follow-up. Patients can also choose to follow-up with an eye care provider not on our list. In that instance we would require a record release to be signed by the patient for the purpose of having access to their follow-up records throughout the study. Prior to all follow-up visits, patients in the enhanced group who have scheduled an appointment will receive a personal phone call reminding them to attend. These patients will receive any necessary interpretation services and educational materials.

*Group 2: Usual Care:* Patients randomized to Group 2 will be recommended to follow-up for eye care with a local eye care provider. These patients will be provided a list of eye care providers to choose from for follow-up. Patients can also choose to follow-up with an eye care provider not on our list. In that instance we would require a record release to be signed by the patient for the purpose of having access to their follow-up records throughout the study. Group 2 represents a realistic choice currently available for patients. Practice patterns will vary depending on the resources, staff time, and services available within each local eye care providers practice.

**C.7.a. Sample Size Determination:** As shown in Figure 1, we have based our sample-size calculations on the current preliminary CDC-project results as well as telemedicine statistics. We project that 30% of those fundus photographs will be abnormal and that, of those, 40% of patients will likely agree to consent and enroll in the study. These patients will be randomized to either the Enhanced Intervention Group 1 or Usual Care Group 2.

**Figure 1: Sample Size Determinates for Randomization**

**C.7.b. Randomization Groups:** The biostatistician, will randomize patients who meet the inclusion criteria with a fixed scheme 1:1 allocation ratio to the 2 study groups. Eligible patients will be consented and randomized to either the usual care group or the enhanced intervention group using the method of random permuted blocks.

**C.7.c.** The following two sites have eye care providers and all patients of these sites will receive initial and follow-up care throughout this study within these specific sites. As a result of this situation the following two sites will differ slightly from the other sites in terms of randomization and intervention:

Philadelphia Department of Public Health - Health District #5 (All Patients Usual Care): Patients will not be randomized at this site, they will all be assigned to usual care. Patients will be seen only by the eye care provider at Health District #5 for their follow-up eye care. They will be scheduled for their first appointment within 4 to 6 weeks from the date of Visit 2 and will then be responsible for scheduling the remainder of their follow-up appointments.

PHMC - Mary Howard Health Center (All Patients Intervention): Patients will not be randomized at this site, they will all be assigned to intervention. Patients will be seen by the eye care provider at Mary Howard Health Center. They will be scheduled for their first appointment within 4 to 6 weeks from the date of Visit 2. Prior to all follow-up appointments a patient navigator will call and remind them about the date and time of their next appointment. The navigator will also be available to answer any insurance questions they may have or help to arrange transportation to their appointments.

C.8. Patient Navigation Protocol (Appendix I): The use of patient navigators and social workers has proven successful in cancer care programs, showing higher rates of follow-up care, while increasing patient satisfaction and decreasing anxiety. Patient navigation shows promise as the missing link between available services and healthcare delivery to vulnerable populations. By educating and guiding patients, navigators can lessen the disparities among racial/ethnic groups at risk for eye disease. Our study staff, project managers, ocular technicians, and research assistants have been trained to serve as patient navigators. Their responsibilities will include: phoning patients to schedule appointments; confirming appointments by mailings, emails and/or text messaging; arranging transportation through Customized Community Transportation (CCT) and Philadelphia Paratransit Service; and scheduling trained medical interpreters.

Wills Eye ocular technicians will also assist patients in the enhanced intervention group across 17 sites with medication refills and obtaining free medications from pharmaceutical companies. Our patient navigators can identify cultural and language differences and are aware of health literacy issues. We will also provide multiple outreach strategies as additional barriers are identified. Results will be discussed at our weekly research team meetings, quarterly meetings with each partner, and annual meetings with our Advisory Board.

C.8.a. Identifying Barriers to Follow-up Using Social Workers: Research shows that individuals at high risk for glaucoma are not likely to participate in screening programs or ongoing follow-up with an ophthalmologist in an office-based setting. Appendix J describes how innovative approaches to identifying and remediating barriers have been accomplished in our current CDC glaucoma detection program and can be tested, refined, and implemented in this proposed study (Section C.2.a). Educational materials may help non-adherent patients to understand the benefits of taking glaucoma medications regularly.

In the same way that social-work interventions have proven beneficial for patients with cancer, such interventions can enhance outcomes in those affected by glaucoma and other eye diseases. Medical social workers understand and value a patient's right to self-determination. They can work with patients directly to empower them to seek appropriate methods of treatment and follow-up vision care. Therefore, we have budgeted for one part-time, medical social worker who will assist the research team with identifying cultural, racial/ethnic, costs, trust, and language barriers as described by Bentacourt. She will work interact with any social workers employed at the FQHCs; supervise, train, and mentor the patient navigators; and contact patients enrolled in the enhanced intervention group. By testing and refining our approaches to removing these barriers, we hypothesize that patient navigators and a social worker will significantly improve patients' follow-up vision care, patient satisfaction, and quality-of-life.

C.9. Management and Follow-up Visits 3-8: To ensure that all patients receive appropriate treatment and that outcomes are tracked yearly, adherence to follow-up eye care access and utilization will be our primary outcome measure. All patients who fulfill the inclusion criteria, have consented, and completed Visit 2 will be randomized and either referred or scheduled (depending on assigned randomization) for Visit 3 within 4 weeks with a local, general eye care provider or earlier at the glaucoma specialist’s discretion. All medical records from our confirming diagnostic exam will be faxed to the local eye care provider who will examine the patient. A form acknowledging receipt of records by the local eye care provider will be requested (requiring signature). Participating eye care providers will be informed about the study during Phase 1 and blinded to the patient’s intervention group. We will refer patients diagnosed with glaucoma or glaucoma suspect to an office that is able to conduct visual field testing.

During Visit 3 the eye care provider will assess the patient’s ocular, systemic, and family history and conduct a eye exam that includes: 1) best correct visual acuity measurement using Snellen eye charts, 2) slit-lamp biomicroscopy of the anterior segment, 3) intraocular pressure (IOP), 4) optic nerve head evaluation, 5) central corneal thickness measurement, 6) visual field analysis using a visual field analyzer (such as Octopus or Humphrey), and 7) gonioscopy (Table 5). Based on these results, the ophthalmologist will reconfirm their ocular diagnosis and adjust therapy as needed. Most individuals will be recommended at the appropriate follow-up intervals shown in Table 6. In conjunction with our general ophthalmology advisor and the CDC, we will plan and develop definitions of adherence for all patients during Visits 3-8. Follow-up recommendations for other eye disease diagnoses will also be made using standard *AAO Practice Pattern Guidelines*.

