**D.1.b. Effectiveness/Efficacy:** We will evaluate the impact of our enhanced intervention on our proposed outcomes, including quality-of-life, and economic efficiency. Determining the effectiveness of our intervention is critically important because patients with undetected glaucoma and other eye diseases can suffer lasting visual impairment that can affect their quality-of-life, economic status, morbidity, and ultimately mortality. New strategies are necessary to improve patient access and utilization of eye care. Our study aims to determine if adherence to follow-up recommendations changes as a result of the enhanced intervention. We will determine the effectiveness of the intervention by examining the effect size associated with our intervention and specified outcomes (adherence to follow-up recommendations and vision-related quality-of-life).

**D.1.c. Adoption:** Our letters of support from Advisory Board members and partner institutions demonstrate a strong commitment and willingness to participate in this research study. We are working closely with primary care offices, health centers, universities, governmental agencies, and community organizations. We expect to notice variations in patient behavior based on the number of resources available to them. These varying settings and intervention modalities are critical to the current and potential impact of our intervention. If differences exist among sites, this is evidence of differential adoption.

**D.1.d. Implementation:** At each setting, implementation refers to the intervention agents' fidelity to all elements of the protocol. This includes consistency of delivery as intended and the time and cost of the intervention. Investigators in coordination with Westat and the project manager will determine the extent to which the intervention was delivered. We will assess implementation by reporting on the percentage of process objectives that were achieved, such as: What proportion of patients received the confirming diagnosis enrolled in the study? How many patients followed up with the general ophthalmologists at the initial 6-month, 1-year, 2-year, and 3-year visits. We will also conduct a cost analysis and report costs of all levels of the intervention, including recruiting patients, reading images, confirming diagnoses, randomization, and 3-year follow-up (Table 7).

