**Table 9: Assessment of Adherence to Follow-Up Recommendations**

Recommended Follow-up	Number of visits per year considered adherent to recommendations
1-2 months	At least 6 visits per year with an eye care provider
3-6 months	At least 3 visits per year with an eye care provider
6 months	At least 2 visits per year with an eye care provider
12 months	At least 1 visit per year with an eye care provider

E.2.c. Primary Analysis for Aim 2: The primary outcome of the study is adherence to recommended follow-up in each year as described in section E.1.c. For each of the 3 years of follow-up, we have a dichotomous measure of adherence. We will model this longitudinal dichotomous outcome using Poisson regression within a generalized estimating equation (GEE) framework. Our model will include time (Year 1, 2, and 3), randomization assignment, randomization by treatment interaction, and baseline individual characteristics believed to be associated with adherence to follow-up, including age, diagnosis, vision impairment, and overall vision-related quality-of-life. Within this model, we will test 2 hypotheses.

First, we will compare randomization groups at Year 1 to test whether there are differences in early adherence. Second, we will calculate the average effect of randomization across Years 2 and 3 and test the long-term efficacy of the intervention. In both cases, we will estimate the overall relative risk of adherence along with its associated confidence interval. Each test will be performed with alpha=0.025. The primary analysis will include all patients who were randomized and have some adherence data (see section on missing data below).

E.2.d. Power for the Primary Analysis for Aim 2: Our estimated available sample size is given in Figure 2. We will randomize 300 patients (150 per group). Assuming up to 10% dropout where adherence cannot be calculated due to death or study withdrawal (i.e., final analysis dataset of n=135 per group), we calculate power to detect a 20% improvement in adherence under various assumptions of adherence under Usual Care. We have greater than 80% power to detect these differences using a two-sided chi-square test with alpha=0.025 (Table 10).

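### Randomisation names no site stratum and the primary model omits site and partner organisation, which forgoes a small gain in balance and precision

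*Combined protocol and SAP*

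**What the plan says.** **Allocation.** C.7.b gives a "fixed scheme 1:1 allocation ratio to the 2 study groups", with patients "randomized to either the usual care group or the enhanced intervention group using the method of random permuted blocks". No stratification factor is named there or elsewhere. C.7.c exempts two sites: at one every patient gets usual care, at the other every patient gets the intervention.

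**Analysis.** E.2.c states: "Our model will include time (Year 1, 2, and 3), randomization assignment, randomization by treatment interaction, and baseline individual characteristics believed to be associated". The characteristics it goes on to name are age, diagnosis, vision impairment and vision-related quality of life. Site and partner organisation are absent, and they are also absent from the models in E.2.e and E.2.f.

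**Setting.** C.4.a has 7 primary care offices and 10 health centres, and C.8 refers to "patients in the enhanced intervention group across 17 sites". C.4.b names four partner organisations and says that each runs its own system for detecting and referring eye patients. D.1.c says "We expect to notice variations in patient behavior based on the number of resources available to them" and then "If differences exist among sites, this is evidence of differential adoption".

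**The concern.** The plan anticipates that patients in different settings will behave differently, and the primary outcome (attendance at recommended visits) is a behaviour. A factor expected to predict the outcome would normally be used as a stratum and carried into the model. Here it is used in neither.

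Two things are at stake. First, arms can be unbalanced within a site by chance, which invites the question whether a difference in adherence reflects which clinics supplied each arm. Second, any between-site variation stays in the error of the estimated relative risk.

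**Working it through.** **Inputs.** From E.2.d and Table 10: 300 randomised, 135 per arm analysed after 10% dropout, two-sided alpha 0.025 per test, 20-point difference. From C.4.a and C.7.c: 17 sites, 2 of them not randomised, so 15 randomising. Assumed, because the documents give no figure: equal site sizes (270/15 = 18 analysed patients) and between-site SDs in usual-care adherence of 0, 5, 10 and 15 points.

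**1. The plan's own power.** A pooled-variance two-sided chi-square test without continuity correction, n = 135 per arm, gives 86.1, 85.7, 86.1, 87.2, 89.1 and 91.6%. Table 10 states 86, 86, 86, 87, 89 and 92%. All six rows reproduce.

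**2. Analytic gain, 35% vs 55% row.** The share of outcome variance between sites is ICC = SD² / [p(1 − p)], with p = (0.35 + 0.55)/2 = 0.45 and p(1 − p) = 0.2475. If adjustment removes all of it, effective n per arm = 135/(1 − ICC).

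| Site SD | ICC | Effective n per arm | Power |
|---|---|---|---|
| 0 | 0 | 135 | 86.1% |
| 5 points | 0.0025/0.2475 = 0.010 | 136.4 | 86.5% |
| 10 points | 0.0100/0.2475 = 0.040 | 140.7 | 87.6% |
| 15 points | 0.0225/0.2475 = 0.091 | 148.5 | 89.4% |

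**3. Simulated gain, same row.** 15 sites of 18 patients, beta-distributed site rates, 100,000 trials per setting. The unadjusted test is the chi-square; the site-adjusted test is Mantel-Haenszel, standing in for the Poisson GEE in a single year.

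| Site SD | Unstratified, unadjusted | Stratified and adjusted | Unstratified, adjusted for 15 sites |
|---|---|---|---|
| 0 | 85.7% | 85.8% | 84.1% |
| 5 points | 85.5% | 86.1% | 84.2% |
| 10 points | 85.8% | 87.6% | 85.7% |
| 15 points | 86.1% | 89.4% | 87.8% |

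A repeat with a new random seed gave 85.9% to 89.5% at SD 15. The gain from doing both is therefore about 0 to 4 points. The last column shows that adjusting for 15 sites that were never strata costs 85.7 − 84.1 = 1.6 points when sites do not differ, and 85.5 − 84.2 = 1.3 points at SD 5.

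**4. Type I error.** Nominal one-tail error is 0.0125. The unstratified, unadjusted test gives 0.0127 (SD 10) and 0.0128 (SD 15). Stratifying without adjusting gives 0.0114 and 0.0096, which is conservative. Stratifying and adjusting gives 0.0126 and 0.0123. So the two changes belong together.

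**5. Balance.** If each patient's arm were an independent coin flip, 2 × P(Bin(18, 0.5) ≤ 6) = 0.238. Permuted blocks do better when consecutive patients come from one site. With assumed blocks of 4 to 8, a simulated central list gives 12:6 or worse with probability about 22–23% if patients from all sites arrive singly in random order, 10–16% in runs of 3 per site, and 0–7% in runs of 6. Hence 24% is an upper bound.

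**6. The two non-randomised sites.** If they are pooled with the randomised patients, bias in the adherence difference ≈ (share of each arm) × (gap in underlying adherence between the two sites). With assumed shares of 5 to 15% and gaps of 10 to 20 points, this runs from 0.05 × 10 = 0.5 to 0.15 × 20 = 3 points. Adjusting for site as a fixed effect would leave these patients with no information about the arm effect.

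**The case against.** The strongest case against is that this is a small preference resting on thin evidence. Its main points, and what stands of each:

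- **Evidence that site matters.** A reader might take C.7, "Practice patterns will vary depending on the resources, staff time, and services available within each local eye care providers practice", as showing that recruiting sites differ. It does not: it concerns eye care providers, whom patients in both arms choose from a list or find elsewhere, so a recruiting-site stratum would not control that variation. D.1.c is also conditional about site differences. This stands: site is an expected source of variation, not a known one. C.4.b and the first D.1.c statement are enough to make stratification sensible.
- **Imbalance.** Under C.9 most patients are randomised after Visit 2, and under C.6 a team travels to a site for the day to run that visit. Patients would then tend to arrive in runs by site, so even a central blocked list would give some balance within site. This stands, and is why 24% is quoted only as a ceiling.
- **Size.** Planned power is already 86 to 92%. C.4.a gives 374 randomised rather than 300; with 10% dropout (187 × 0.9 ≈ 168 per arm) power would be about 93 to 96%, and the gain smaller still. This stands.
- **Silence.** C.7.b does not rule out blocks kept by site. That is fair, but if they were, the plan should say so and the model should carry the factor. The covariate list in E.2.c is open-ended, but only for individual characteristics.

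**Conclusion.** The point holds as one of efficiency and balance. The plan expects patients and referral systems to differ by setting and partner, names no stratum, and leaves site and partner organisation out of its models. Stratifying and adjusting together would add about 0 to 4 power points in the 35% vs 55% row over assumed between-site SDs of 0 to 15 points, at no loss of power if sites do not differ. These figures rest on equal site sizes, 15 randomising sites and an assumed between-site SD.

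A reader might infer that the primary test is invalid or that Table 10 overstates power. Neither follows: among randomised patients the type I error of the planned approach is close to nominal, and Table 10 reproduces. The two C.7.c sites are a different matter. Arm and site are fully confounded there, and no stratum or covariate can repair that.

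**What to change.** - **C.7.b:** randomise in permuted blocks within each randomising site, or within partner organisation where sites are too small to fill blocks. Vary block size at random, because staff who deliver the navigation know the assignments and could anticipate the end of a fixed block.
- **E.2.c and E.2.e:** include the same stratification factor as a covariate.
- **If lists have already been issued without site strata:** adjust for partner organisation rather than for every site. Four named partners mean three indicator terms, whereas adjusting for 15 unstratified sites can cost 1 to 2 power points. If blocks were in fact kept by site, say so and carry site into the models.
- **C.7.c:** apply all of this to randomised patients only. Keep the two non-randomised sites out of the randomised comparison and report them separately.

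The cost is separate allocation lists and a few model parameters. Incomplete blocks at small sites would give back some of the balance, which is the reason for allowing partner organisation as the stratum.

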**Table 7: Tracking Measures Using *RE-AIM Framework* Approach**

RE-AIM	Evaluation Question	Tracking Measures	Data Source
Adoption	How were community partners and primary care settings engaged in the study?	# of participating community partners and primary care settings (offices, health centers). Primary care offices' satisfaction with participation.	Contact log  On-site observations On-site interviews

Reach	To what extent are high risk target populations being reached?	Patient characteristics (demographics, insurance status, ocular history, ocular risk factors).	Intake form/EMR
Implementation	How was the program implemented?	Patient navigator, cultural competency training conducted. # of staff at each onsite activity. # of patients who follow up with general ophthalmologists. Time taken per patient and for each eye exam. # of confirmatory diagnosis from fundus photos. # of referrals made based on NEI-VFQ.	Planning log  On-site observations  EMR
Efficacy/ effectiveness	Did the intervention work? (Comparison between intervention and control groups)	# of patients from each group adhering per year. Average percentage of visits attended per year. Clinical measures (visual acuity, IOP, VF). Health related quality-of-life (Visits 2 and 8). Satisfaction with eye services at each visit.	EMR  EMR NEI-VFQ Patient satisfaction survey
Maintenance	To what extent has the program been institutionalized?	Willingness of partners and PCPs to continue with telemedicine and community model.	On-site interviews

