### Table 8: Process Measures to Be Tracked

Process Measures	Phase 1 Plan, Develop Detection	Phase 2 Confirm Diagnosis Follow-up	Phase 3 Follow-Up Disseminate Replicate
# of partners and primary care offices for recruitment sites	✓		
# of patients received by each primary care offices and health centers	✓		
# of letters mailed/calls made to patients from recruitment and Visit 1	✓		
# of patients scheduled, confirmed, attended detection eye exam Visit 1-2	✓	✓	
# of patients who cancelled and assessment of barriers to attending exam	✓	✓	✓
# of patients/doctors sent letters with normal/abnormal eye exam results	✓	✓	✓
# of patients diagnosed with glaucoma, suspect, and other eye diseases	✓	✓	✓
# of patients who attended exams with an ophthalmologist (Visits 3-8)		✓	✓
# of patients recommended to follow-up in 1-2 weeks, 1-2 months, 3-6 months, 6 months, and 12 months from baseline Visits 2-8		✓	✓
# of people prescribed ocular medication, laser therapy, or eye surgery		✓	✓
# of patients who requested medication assistance for eye drops	✓	✓	✓
# of patients who requested and used translation/interpreter services	✓	✓	✓
# of patients who requested and used transportation services	✓	✓	✓
# of referrals for a low-vision specialist, cataract surgeon, etc.		✓	✓
# of referrals for a Medicare/Medicaid advisor or to complete application		✓	✓

**E.1.d. Patient Satisfaction Surveys:** With Westat, the CDC and Advisory Board members, we will develop brief questions regarding the patient's satisfaction. We will survey patients at the conclusion of all visits. Wills Eye research staff will administer surveys during the detection and baseline visits. We hypothesize that satisfaction will be greater for those in the intervention group than in the usual care group.

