E.3.b. Effectiveness Measure for Aim 3: In addition to conducting a comprehensive examination of costs, we will systematically examine these costs in the context of the intervention's societal benefits by conducting a formal cost-effectiveness analysis. The cost-effectiveness analysis will employ quality-adjusted life years (QALYs) as the primary measure of societal benefits. We will capture QALY over the course of 2 years using the Health Utilities Index, v.2/3 (HUI-2/3). HUI-2/3 is a utility measurement instrument that consists of 15 items that capture 8 attributes of health-related QoL: vision, hearing, speech, ambulation, dexterity, emotion, cognition, and pain.

The scoring algorithm will be obtained from Health Utilities, Inc. and is based on Canadian health preference weights. Utility scores from this instrument range from 0-1, with a higher score indicating better quality-adjusted life. Previous research has shown that the HUI-3 has consistent validity in people with glaucoma, diabetic retinopathy, and cataracts. QALY will be measured as the amount of utility gained or lost over each year of the program.

E.3.c. Incremental Cost-Effectiveness Ratio: The primary cost-effectiveness measure will be defined as the incremental difference between cost of the enhanced intervention and usual care, divided by the difference in health utility-Incremental Cost Effective Ratio (ICER). The ICER thus will indicate the additional costs to bring about one additional unit of benefit (QALY) from the enhanced intervention compared to usual care. The

reference case, which will be defined as usual care. The ICER obtained will be compared to acceptable thresholds of \$50,000 to \$100,000-QALY. A secondary measure will be cost per diagnosis made.

E.3.d. Sensitivity Analysis for Aim 3: To account for uncertainty in our primary ICER, cost and effectiveness data will be entered into a decision analytic model. This is particularly important since the study will be powered based on the primary outcome, not the cost-effectiveness measure. Sensitivity analyses will ensure robustness of the ICER. Both univariate sensitivity analysis (whereby 1 variable is changed at a time and impact on the ICER will be examined), and probabilistic sensitivity analysis (PSA), whereby all relevant variables are simultaneously modified within reasonable ranges will be conducted. Sensitivity analyses will include those variables where we anticipate “real world” uncertainty.

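### Two sites assign every patient to one arm without randomisation, and the cost-effectiveness comparison (less clearly, satisfaction and Table 7) does not exclude them

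*Combined protocol and SAP*

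**What the plan says.** **Assignment.** C.7.b describes 1:1 allocation by permuted blocks. C.7.c then makes an exception for two sites that have their own eye care providers. It announces that "the following two sites will differ slightly from the other sites in terms of randomization and intervention". For the first site: "Patients will not be randomized at this site, they will all be assigned to usual care". For the second: "Patients will not be randomized at this site, they will all be assigned to intervention". No visible section says how the patients of these two sites are to be analysed. C.7.a and C.9 say that enrolled patients are randomised and mention no exception.

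**Care within the arms.** In C.7, Group 2 patients are advised to follow up and given a list of providers. At the usual-care site in C.7.c, the first appointment, with the site's own provider, is scheduled for them within 4 to 6 weeks of Visit 2.

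**Comparisons.**
- E.3.c defines the primary cost-effectiveness measure from the "incremental difference between cost of the enhanced intervention and usual care", divided by the difference in health utility.
- E.1.d states: "We hypothesize that satisfaction will be greater for those in the intervention group than in the usual care group".
- The effectiveness row of Table 7 asks "Did the intervention work? (Comparison between intervention and control groups" and lists, among its measures, the number "of patients from each group adhering per year".

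None of the three says which patients make up each group.

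**The concern.** In the randomised patients, a difference between arms can be attributed to the intervention. In the C.7.c patients it cannot. Everyone in usual care comes from one site and everyone in intervention from the other, so patient mix, provider and local access differ along with the arm. Covariate adjustment for site does not help, because neither site contains a contrast between arms.

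C.7.c gives these patients the same arm labels as the randomised patients. A comparison defined only by arm label can therefore take them in, and the analyst would not be departing from the plan. Most is at stake in Aim 3. Hypothesis 3 rests on the incremental ratio, and costs depend directly on how and where follow-up is provided. The usual-care label would also cover two kinds of comparator: a scheduled on-site first visit at one site, and advice plus a list elsewhere.

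**Working it through.** The plan gives no figure for this point, so the check is to read the analysis sections side by side and then see what pooling would do.

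**1. Which analyses are limited to randomised patients?**

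| Section | Comparison | Population wording |
|---|---|---|
| E.2.b | Aim 2, general approach | By randomised assignment, however much intervention was received |
| E.2.c | Aim 2 primary, yearly adherence | Randomised patients with some adherence data |
| E.2.e | Aim 2 secondary: visit counts, clinical and quality-of-life measures | Randomisation assignment is the model term |
| E.2.g | Longitudinal models | All randomised patients |
| E.3.c | Incremental cost-effectiveness ratio | Arm names only |
| E.1.d | Satisfaction hypothesis | Arm names only |
| Table 7, effectiveness row | By-group tracking measures | Arm names only |

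The first four rows leave out never-randomised patients on their plain wording. The last three do not.

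**2. What would pooling do?** Let s be the share of each arm that comes from its C.7.c site (taken as equal in both arms for simplicity), D the arm difference in randomised patients, and d the difference between the two C.7.c sites. Then:

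- pooled difference = (1 − s) × D + s × d
- error relative to the randomised comparison = s × (d − D)

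For the cost-effectiveness ratio this applies to the numerator and the denominator separately:

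- pooled ratio = [(1 − s) × D_cost + s × d_cost] / [(1 − s) × D_utility + s × d_utility]

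The ratio can move either way. If the utility difference is small, a modest shift in the denominator can matter a great deal.

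**3. Can s and d be filled in?** The documents give neither. For s, an illustration needs two assumptions: that the two sites are among the 17 (7 primary care offices and 10 FQHCs in C.4.a; 17 sites in C.8), and that recruitment is even. With N enrolled patients, each site contributes N/17 and each arm holds N/2, so s = (N/17)/(N/2) = 2/17 = 0.118, or 11.8%. For d there is no basis in the documents for cost, utility or satisfaction. The error therefore has no defensible numerical value.

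**4. What would exclusion cost?** On the same two assumptions, leaving out two of 17 sites removes 2/17 = 11.8% of the patients from each comparison that would otherwise have pooled them.

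**The case against.** **The groups are introduced as randomised.** C.4.a and C.7 describe them that way, and the survey notes in Table 5 and C.6.b tie follow-up surveys to randomisation. This supports the intended reading but does not settle it. C.7.c uses the same arm names for patients who are not randomised, and the survey notes concern administration, not analysis.

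**RE-AIM may not be a separate analysis.** D.1.b names adherence and vision-related quality of life, and E.2.c and E.2.e analyse both by randomisation assignment. Table 7 is a list of tracking measures with no model or test. This largely stands: D.1.b can be read as posing a question that E.2 answers. What remains is the by-group counting in Table 7. Satisfaction is likewise a single hypothesis sentence with no stated test. Both are weaker instances than E.3.c.

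**The two sites are alike on paper.** Both have on-site providers and both schedule the first appointment within 4 to 6 weeks. The difference described between them is navigator help, which is the intervention. The scheduled first visit also matters less for adherence, because E.2.b counts Visit 4 and later. This is fair, and it is why no large gap should be presumed. Patient mix and provider may still differ, and E.3 does not restrict costs to Visit 4 and later.

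**C.7.c is a named exception to a general rule.** Nobody would randomise at these sites because of C.9. Agreed. The mismatch is one of consistency, and a cross-reference resolves it.

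**Exclusion is partly a preference.** D.1.c expects variation between sites, and results with and without the two sites could be shown. Descriptive reporting by site serves D.1.c. A pooled result would still not estimate the intervention effect without bias.

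**Conclusion.** The point holds, mainly for the Aim 3 cost-effectiveness ratio and less clearly for satisfaction and Table 7. As written, these comparisons can take in patients whose arm is fixed by their site, and so present a site difference as an intervention effect. Its size and direction are not determinable from the documents. The only figure offered, 11.8%, is a share of patients under assumed even recruitment, not a bias.

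Three stronger readings are tempting and not supported:

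- *The primary adherence result is biased.* E.2.b, E.2.c, E.2.e and E.2.g are worded for randomised patients.
- *The trial loses power.* A reader might note that 2,500 × 30% × 40% = 300, with no deduction for the two sites, and infer that their patients count toward the target. E.2.d says that 300 patients will be randomised, which on plain words leaves out patients who never are. Figures 1 and 2 are not visible and may show a deduction. Table 10 reproduces at 135 per group (85.7% to 91.6%), and this point gives no reason to change it.
- *The bias is a stated number of adherence percentage points.* Any such number needs an invented site share and site gap, for an outcome whose only specified models already use randomised patients.

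**What to change.** Add one sentence to E.3, E.1.d and the effectiveness row of Table 7, to this effect: *between-arm comparisons include only patients who were randomised; patients enrolled at the two C.7.c sites are reported separately and descriptively, by site.* Repeat the analysis rule in C.7.c, where the exception is created. Add the exception to C.7.a and C.9 so that their statements on randomisation agree with C.7.c.

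The wording should be settled before the Aim 3 data are analysed. It changes no site arrangement, no patient's care and no part of the Aim 2 models. The cost is a few sentences and somewhat fewer patients in the comparisons that would otherwise have pooled them, about 12% under the assumptions shown in the working.
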